11.2.2 Jump to Reference (J2R)

The dataset will first be imputed to monotone missing using PROC MI with the MCMC and impute=monotone option. Imputation will be carried out 1000 times and any internal missing observations, including missing baseline covariates and intermediate missing in the response variable will be replaced with the average across all imputations.

For the resulted data with monotone missing, the following steps will be used to create imputed datasets:

- (1) Data from all subjects will be used to fit a multivariate normal distribution with unstructured mean and unstructured variance using a Bayesian approach with a noninformative prior for the mean and a conjugate prior for the variance covariance matrix.

- (2) Draw a pseudo-independent sample for the linear predictor parameters and the covariance parameters from the joint posterior distribution obtained in step (1). Both steps (1) and (2) will be done using PROC MCMC in SAS.
- (3) Use the linear predictor parameters and the covariance parameters obtained in step (2) to construct new mean vectors separately for each treatment group (placebo and BIIB092). Specifically, the newly constructed mean vector for someone on treatment group T whose last observed visit was visit k is calculated as

$$\mu_T^{(k)} = \begin{cases} \mu_{i,T}, & \text{if } i \leq k \\ \mu_{i,P}, & \text{if } i > k \end{cases}$$

Here P represents the placebo group. For subjects with no post-baseline records, or subjects on the placebo group, the newly constructed mean vector is the same as the placebo mean. Using $\mu_T^{(k)}$ from step (3) and covariance parameters from step (2), find the conditional normal distribution of the visit with missing data, and use this conditional distribution to impute the missing data.

11.2.3 Pattern Mixture Model

Subjects will be assigned one of the following three patterns:

1. Completer: subjects with no missing data at Week 12, 24, 26, 48 and 52 for primary endpoints and at Week 12, 24, 36 and 52 for key secondary endpoints;
2. Subjects who withdrew due to reasons that may be related to efficacy, including lack of efficacy, subject request to discontinue study treatment, subject withdrew consent, poor/non-compliance, death, and withdrawal by caregiver;
3. All the other subjects with missing data.

The dataset will first be imputed to monotone missing using PROC MI with the MCMC and impute=monotone option. Imputation will be carried out 1000 times and any internal missing observations, including missing baseline covariates and intermediate missing in the response variable will be replaced with the average across all imputations.

For the resulted data with monotone missing, the following steps will be used to create imputed datasets:

- (1) Subset subjects in pattern 1 and pattern 2, and impute the missing data using the copy increment from reference method described in Section 10.2.1.
- (2) Subset subjects in pattern 1 and pattern 3, and impute the missing data using PROC MI with the MONOTONE REG option.
- (3) Combined datasets obtained in steps (1) and (2).

11.3 Adverse event of special interest custom search criteria

Immunogenicity is an AESI in the BIIB092 clinical development program. Adverse events representing potential immune/hypersensitivity reactions will be identified using the following customized MedDRA search criteria:

- Anaphylactic reaction SMQ narrow and broad
- Angioedema SMQ narrow and broad

- Severe cutaneous adverse reactions SMQ narrow and broad
- Eosinophilia (PT terms: Eosinophilia; Eosinophil count increased; Allergic eosinophilia; Pulmonary eosinophilia)
- Miscellaneous terms
 - Cytokine release syndrome PT
 - Infusion related reaction PT
 - Infusion site reaction PT
 - Allergic conditions NEC HLT
 - Drug hypersensitivity PT
 - Documented hypersensitivity to administered product PT
 - Vasculitis PT
 - Systemic Lupus erythematosus PT
 - Rheumatoid arthritis PT
 - Antibody test positive PT
 - Antibody test abnormal PT
 - Antibody test PT
 - Drug specific antibody present PT
 - Neutralising antibodies PT
 - Neutralising antibodies positive PT
 - Non-neutralising antibodies positive PT
 - Respiratory dyskinesia PT

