3.2 Analysis Period

Depending on the purpose, different analyses will be conducted on the following study periods:

1. **OLE period**. Only data in the OLE period will be included in these analyses. This OLE analysis period will be applied to all the AE analyses, and the analyses will include all subjects who were dosed in the OLE period.
2. **Placebo-controlled and OLE period**. All the data in the placebo-controlled and OLE periods will be included in these analyses. This analysis period will be applied to all efficacy analyses. The analyses will include all subjects who were dosed in the study including those who did not enroll into the OLE period.
3. **Active treatment (placebo-controlled and OLE) period**. The active treatment period is defined as the study period(s) in which a subject received BIIB092. For early start subjects, all data from placebo-controlled and OLE periods will be included. For late start subjects,

only data in the OLE period will be included. This analysis period will be applied to all safety analyses, and the analyses will include all subjects who were dosed in the study except for subjects who received only placebo in the placebo-controlled period and did not get dosed in the OLE period.

For a given output, both the analysis population and the analysis period will determine which subjects will be included. For example, the incidence table of adverse events in the OLE period will include subjects in the safety population for the OLE period, i.e., all randomized subjects who received at least one dose of study treatment in the OLE period. The incidence rate table of adverse events in the active treatment (placebo-controlled and OLE) period will include subjects in the safety population for the active treatment period, i.e., all randomized subjects who received at least one dose of treatment in the active treatment period. In this SAP we do not separately define the analysis population in each analysis period.

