6.2.4 Adverse event of special interest

Immunogenicity is an AESI in the BIIB092 clinical development program. Adverse events representing potential immune/hypersensitivity reactions will be identified using customized MedDRA search criteria: Anaphylactic reaction, Angioedema, and Severe cutaneous adverse reactions via SMQ (narrow and broad) search; Eosinophilia, and Miscellaneous terms. Further details are given in Appendix 11.1.

An incidence proportion table for potential immune/hypersensitivity reactions organized by SMQ/Miscellaneous categories and by PT (for both AEs and SAEs), and similarly for potential immune/hypersensitivity reactions for subjects with and without treatment emergent positive anti-drug antibody (ADA) results will be presented for both AEs and SAEs for the OLE Period. Positive treatment emergent ADA will be based on the definition in Section 8 using the integrated placebo-controlled and open label extension data.

An exposure adjusted incident rate table will be provided for the active treatment (placebo-controlled and OLE) period.

The following analyses (incidence proportion only) will be performed for the OLE period to explore the relationship between ADAs and the safety of BIIB092:

- AEs for subjects with and without positive treatment emergent ADAs
- SAEs for subjects with and without positive treatment emergent ADAs

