11.1 Adverse event of special interest search

The following search will be performed using MedDRA 22.0.

- Anaphylactic reaction SMQ narrow and broad
- Angioedema SMQ narrow and broad
- Severe cutaneous adverse reactions SMQ narrow and broad
- Eosinophilia (PT terms: Eosinophilia; Eosinophil count increased; Allergic eosinophilia; Pulmonary eosinophilia)
- Miscellaneous terms
 - Cytokine release syndrome PT
 - Infusion related reaction PT
 - Infusion site reaction PT
 - Allergic conditions NEC HLT
 - Drug hypersensitivity PT
 - Documented hypersensitivity to administered product PT
 - Vasculitis PT
 - Systemic Lupus erythematosus PT
 - Rheumatoid arthritis PT
 - Antibody test positive PT
 - Antibody test abnormal PT
 - Antibody test PT
 - Drug specific antibody present PT
 - Neutralising antibodies PT
 - Neutralising antibodies positive PT
 - Non-neutralising antibodies positive PT

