6.2.3 Adverse event of special interest

Immunogenicity is an AESI in the BIIB092 clinical development program. Adverse events representing potential immune/hypersensitivity reactions will be identified using customized MedDRA search criteria: Anaphylactic reaction, Angioedema, and Severe cutaneous adverse reactions via SMQ (narrow and broad) search; Eosinophilia, and Miscellaneous terms. Further details are given in Appendix 11.3.

An incidence proportion table for potential immune/hypersensitivity reactions organized by SMQ/Miscellaneous categories and by PT (for both AEs and SAEs), and similarly for potential immune/hypersensitivity reactions for subjects with and without treatment emergent positive anti-drug antibody (ADA) results (as defined in Section 8) will be presented for both AEs and SAEs. A listing of potential immune/hypersensitivity reactions will be provided.

The following analyses (incidence proportion only) will be performed to explore the relationship between ADAs and the safety of BIIB092:

- AEs for subjects with and without treatment emergent positive ADAs
- SAEs for subjects with and without treatment emergent positive ADAs

In this study, additional samples for ADA, referred to as “event driven” samples, may be collected for subjects with hypersensitivity events. A listing of AEs for subjects with any event driven ADA samples will be provided.

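### The two SAPs define the same adverse event of special interest with search lists that differ by one term, Respiratory dyskinesia, so one event can be classified differently across tables and listing

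*SAP*

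**What the plan says.** Both SAPs name a single AESI, immunogenicity, and capture it through a customised MedDRA search for potential immune or hypersensitivity reactions (PC SAP 6.2.3, OLE SAP 6.2.4). Each SAP sends the reader to its own appendix.

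- **PC SAP.** Appendix 11.3 introduces its list thus: "Adverse events representing potential immune/hypersensitivity reactions will be identified using the following customized MedDRA search criteria". The last miscellaneous entry is "Respiratory dyskinesia PT". Section 6.2.3 uses this search for incidence proportion tables of AEs and SAEs, overall and by anti-drug antibody status, and for a listing.
- **OLE SAP.** Section 6.2.4 states "Further details are given in Appendix 11.1". That appendix opens with "The following search will be performed using MedDRA 22.0", and its miscellaneous list stops at "Non-neutralising antibodies positive PT". Section 6.2.4 uses the search for the OLE-period proportion tables and adds a pooled output: "An exposure adjusted incident rate table will be provided for the active treatment (placebo-controlled and OLE) period".

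Two further rules connect the documents. The OLE SAP's section on analysis periods defines the active treatment period so that "For early start subjects, all data from placebo-controlled and OLE periods will be included". OLE SAP 3.1 leaves listings to the PC analysis, where they are to span both periods; PC SAP 3.1 says the same as a general rule.

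**The concern.** An AESI should have one case definition within a trial, because its tables are read side by side. Here the definition depends on which SAP produces the table, and the two SAPs overlap: the extension analysis takes in first-year events that the PC analysis has already classified. The same event in the same BIIB092 subject could be a case in one output and not in another. The AESI listing, produced under the PC SAP, could also contain an extension-onset case that the OLE AESI table omits. Anyone reconciling table with listing would meet an unexplained mismatch in the programme's only named AESI.

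**Working it through.** No sample size, power or significance figure is involved. The check is a term-by-term comparison of the two appendices, followed by a trace of each list to its outputs.

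**1. Compare the lists.**

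| Component | PC SAP 11.3 | OLE SAP 11.1 |
|---|---|---|
| SMQs, narrow and broad | Anaphylactic reaction; Angioedema; Severe cutaneous adverse reactions | Same 3 |
| Eosinophilia preferred terms | 4 | Same 4 |
| Miscellaneous terms | 17 | 16 |
| Terms absent from the other list | Respiratory dyskinesia | None |
| MedDRA version for the search | Not stated | 22.0 |

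The difference is 17 − 16 = 1 term. All 16 OLE entries are in the PC list, so the OLE list is a strict subset.

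**2. Trace the outputs.** Take a subject whose only qualifying event is Respiratory dyskinesia, and suppose that none of the 3 shared SMQs contains that term.

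| Output | Onset in PC period, on BIIB092 | Onset in OLE period |
|---|---|---|
| PC AESI tables (PC SAP 6.2.3) | Counted | Outside the period |
| AESI listing (PC SAP 6.2.3; 3.1 of both SAPs) | Included | Included |
| OLE AESI tables (OLE SAP 6.2.4) | Outside the period | Not counted |
| Pooled AESI rate (OLE SAP 6.2.4) | Not counted | Not counted |
| General AE tables by preferred term (PC SAP 6.2.2; OLE SAP 6.2.2 and 6.2.3) | Counted | Counted |

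The first column concerns early-start subjects only. First-year events in placebo subjects lie outside the pooled period by design. The second column applies to early-start and late-start subjects alike.

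**3. Effect on the pooled rate.** OLE SAP 6.1.4 defines the exposure-adjusted rate as subjects with the event divided by total time at risk. A case's time stops at first occurrence; a non-case's time runs to the last day on study. Let the shorter list give k cases over total time T, and let u be the time from our subject's event to the last day on study. Then:

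- OLE SAP list: rate = k / T
- PC SAP list: rate = (k + 1) / (T − u)

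The shorter list loses one case and adds u to the denominator, so it can only lower the rate.

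**4. Scale.** If all 306 planned BIIB092 participants are dosed, one such subject is 1/306 = 0.33 percentage points of the PC-period AESI proportion. Neither document gives a frequency for this term or for the AESI, so the number of such subjects, and hence the total effect, cannot be derived.

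**The case against.** The strongest reply is that little is lost.

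- **The SMQs may already cover the term.** Three SMQs, searched narrow and broad, are common to both lists, and their member terms are not given. If one contains Respiratory dyskinesia, the event stays an AESI in every table. This stands and makes the effect conditional. It does not remove the inconsistency: the PC entry would then be redundant and the two appendices would still disagree.
- **The event does not disappear.** A reader might infer that it drops out of the extension reporting. It does not. It remains in the general AE tables by preferred term, in the follow-up-adjusted tables for the active treatment period, and in the AESI listing. Only AESI-specific table entries are at risk.
- **The outputs are not like for like.** A reader might infer that AESI frequency would appear to fall between reports from the definition alone. The documents do not support that. The PC output is a proportion and the pooled output a rate per subject-time. The OLE output is a proportion, but in a different population with variable follow-up. These could differ for many reasons.
- **The versions are not shown to differ.** A reader might set MedDRA 22.0 in OLE SAP 11.1 against the allowance for 22.0 or a later version in the PC SAP. That allowance is written for medical history (4.2) and non-drug therapies (4.4.1), not for the AESI search, and it includes 22.0. All that can be said is that PC SAP 11.3 states no version.
- **A reason may exist out of sight.** The PC SAP is version 2.0 and its contents page lists a section on changes from version 1, but the text after Section 9 is blacked out. The absence of a visible rationale therefore cannot be held against the plan.

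The mismatch between working search definitions survives all of these. The infusion-reaction searches in the same two SAPs (PC 11.4, OLE 11.2) are identical term for term, which suggests that common searches were intended.

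**Conclusion.** The point holds as a minor inconsistency. Followed as written, the two SAPs can classify the same event differently between the PC AESI table and the pooled rate, and between the AESI listing and the OLE AESI table. This rests on two assumptions: that no shared SMQ contains Respiratory dyskinesia, and that at least one subject has it as the only qualifying event. The documents settle neither. The direction is known, since the OLE SAP's AESI counts can only be equal to or lower than those under the PC list; the size is not. The outputs affected are descriptive, and no efficacy result, hypothesis test or sample size is touched.

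**What to change.** Use one identical AESI term list and one stated MedDRA version in PC SAP 11.3 and OLE SAP 11.1, and apply them to the PC, OLE and pooled AESI tables and to the shared listing. The simplest way is to add the PC SAP's extra term to OLE SAP 11.1 and to state the version in PC SAP 11.3. If the lists are meant to differ, say why in both appendices and which list governs the listing. Aligning the term costs one appendix line, and stating the version is a short phrase alongside it. No new data are needed.

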11.4 Infusion reactions custom search

- Infusion site reaction
- Infusion site rash
- Infusion site dermatitis
- Infusion site hypersensitivity
- Infusion site photosensitivity reaction
- Infusion site urticaria
- Infusion site eczema
- Infusion site vasculitis
- Infusion site recall reaction
- Infusion related reaction
- Administration site rash
- Administration site dermatitis
- Administration site eczema
- Administration site hypersensitivity
- Administration site urticaria
- Administration site photosensitivity reaction
- Administration site recall reaction
- Administration site vasculitis
- Administration related reaction

- Injection site dermatitis
- Injection site hypersensitivity
- Injection site rash
- Injection site urticaria
- Injection site photosensitivity reaction
- Injection site eczema
- Injection site recall reaction
- Injection site vasculitis
- Injection related reaction
- Immediate post-injection reaction
- allergic reaction to excipient
- reaction to excipient
- cytokine storm
- cytokine release syndrome
- immune-mediated adverse reaction

